8.4.2 Study Drug Preparation and Dispensing

Study drug will be prepared by the site's investigational pharmacist (or designee) per the Pharmacy Manual provided by AADI.

8.4.3 Administration Instructions

Refer to Pharmacy Manual. The rate of IV administration should not exceed 3.3 mg/m²/min. The rate is based on clinical experience with adult participants, as ABI-009 at 100 mg/m² can be safely administered with 30-min IV infusion.

8.4.4 Storage

Storage for the study drug is at 2-8°C in a secure area under restricted access. If the temperature of study drug storage exceeds or falls below this range, this should be reported to AADI and Sponsor and captured as a deviation.

8.5 Dose-Limiting Toxicities

Definition of Dose Limiting Toxicity (DLT):

Any grade 3 or higher toxicity and designated by the principle investigator as definitely or probably related (level of attribution) to the study drug, and occurring within 30 days of study drug dosing, or as specified per toxicity in the protocol.

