1.12 Clinical Experience with ABI-009 in Pediatric Participants

ABI-009 is currently being investigated in a multicenter phase 1 study (ADVL1514) by the Children's Oncology Group (COG) in pediatric participants with recurrent or refractory solid tumors. The aims of the trial will be to establish the maximum tolerated pediatric dose of ABI-009 administered as an intravenous infusion over 30 minutes on Days 1 and 8 of a 21-day cycle, in combination with temozolomide and irinotecan (administered on Days 1-5), and to investigate

the toxicities, pharmacokinetics, and pharmacodynamics of ABI-009 in pediatric participants with recurrent or refractory solid tumors, including CNS tumors. The study uses the Rolling Six escalation/de-escalation design, and the starting dose of ABI-009 is 35 mg/m².

As of Jan 30, 2018, 6 participants have been enrolled and received treatment. Overall, the adverse events observed with ABI-009 in pediatric participants are consistent with those observed in previous clinical studies in adults. The main dose limiting toxicity of ABI-009, administered as a single agent and in combination with cytotoxic agents temozolomide and irinotecan, is grade 3 thrombocytopenia (2 out of 5 participants receiving ABI-009 at 35 mg/m²). As per the protocol de-escalation guidelines, the new cohort of participants will receive an ABI-009 dose of 20 mg/m² in combination with temozolomide and irinotecan.

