8.4.1 Dosage/Dosage Regimen

All participants receive study drug every 5-9 days for 3 weeks.

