9.2 Clinical Laboratory Measurements

9.2.1 Hematology

Blood will be obtained as noted in the Schedule of Events and sent to each site's clinical hematology lab for a complete blood count (hemoglobin, hematocrit, red blood cell count, white blood cell count, white blood cell differential, and platelet count). If values are found to be abnormal, a sample will be collected and these parameters re-evaluated at the next study visit. If blood sample is unusable for testing, a second sample will be requested from the patient provided blood volume total is within safety range.

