10.5 Visit 6: Post-Dosing One-Week Assessment (+/-2 days)

1. Review adverse events.
2. Review epilepsy diary.

3. Investigator opinion regarding seizures recorded: same, worse, somewhat better, better.
4. Record changes to concomitant medications.
5. Perform abbreviated physical examination.
6. Obtain and record vital signs.
7. Collect urine for pregnancy test (if child-bearing potential).
 - a. If positive confirm with blood test
8. Collect blood for clinical laboratory tests (chemistry, hematology).
9. Laboratory assessments as required per the schedule of evaluations
 - c. Complete Blood Count (CBC) with differential and platelet count
 - d. Blood chemistry assessment, including:
 - i. Sodium, potassium, chloride, bicarbonate, calcium, fasting glucose, albumin,
 - ii. Total protein, BUN, serum creatinine.
 - iii. Total bilirubin, AST, ALT, alkaline phosphatase, uric acid, phosphorus,
 - iv. Fasting serum lipid profile (total cholesterol, triglycerides, HDL and LDL)
10. Coagulation assessment, including prothrombin time, partial thromboplastin time, international normalized ratio (PT/PTT/INR)
11. Whole blood rapamycin trough level
12. Administer C-SSRS, QOLCE, and NCBRF

10.6 Follow-up Visits 7, 8, & 9: 30, 60, and 90 Days Post-Dosing (+/-7 days)

1. Review participant diary for compliance and seizure frequency.
2. Safety follow-up labs at Visit 7 per PI discretion following Visit 6 labs.
3. Investigator opinion regarding seizures recorded: same, worse, somewhat better, better
4. Record changes to concomitant medications.
5. Perform abbreviated physical exam (30 days post-doing only).
6. Measure and record height and weight (at final study visit).
7. Obtain and record vital signs (30 days post-dosing only).
8. On final visit (90 days post-dosing) administer C-SSRS, QOLCE and NCBRF

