APPENDIX 1. SCHEDULE OF EVENTS

	SCREENING DAY -14 TO DAY 0*	VISIT 1: DAY 0	VISIT 2: DAY 30**	VISIT 3: DOSE 1	VISITS 4&5: DOSES 2 AND 3	VISIT 6: ONE WEEK POST- DOSING	VISITS 7&8: 30 AND 60 DAYS POST-DOSING	VISIT 9: 90 DAYS POST- DOSING	EARLY PERMANENT DISCONTINUATION
Informed Consent Process	X								
Enrollment Eligibility Checklist	X								
Demographics	X								
Extended Physical Exam	X								
Neurological Exam	X								
Hepatitis C, and Hepatitis B, HIV if necessary ^A	X								
Epilepsy and Medical History	X								
Height, Weight, and BSA	X			X				X	X
Vitals	X		X	X	X	X			
Pulse Oximetry ^F	X		X	X	X				
CBC with Differential ^C	X		X	X	X	X	X ^B (visit 7 only)		X
Serum Chemistries with Coagulation Assessment ^E	X		X	X	X ^B (visit 4 required)	X ^B	X ^B (visit 7 only)		X
Urine Pregnancy ^G	X		X						
Study Continuation Checklist			X	X	X	X	X		
Abbreviated Physical Exam		X	X	X	X	X	X ^D		X
Concomitant Medication Review		X	X	X	X	X	X	X	X
Dispense Seizure Diary and Glossary		X							
Administer QOLCE, NCBRF, & C-SSRS			X			X		X	X
Review Seizure Diary			X	X	X	X	X		X
Investigator Opinion			X	X	X	X	X		
Dosing Checklist				X	X				
Study Drug Administration				X	X				
Adverse Events			X	X	X	X	X	X	X
Whole Blood Rapamycin Level ^H					X	X			X

*Screening may be combined with Visit 1

**Visit 2 may also be Visit 3 Dose 1

^A Hepatitis C (and if necessary, Hepatitis B) test: 2 mL SST gold top tube. HIV seropositivity test, if necessary: 2 mL gold top tube. If testing for all together, can use one 4 mL SST gold top tube.

^B Only if previous chemistries or coagulation profiles are abnormal or are otherwise clinically indicated.

^C CBC with differential: 1 mL EDTA lavender top tubes if testing with blood trough rapamycin levels. If testing alone can collect only 0.5 mL in EDTA tube.

^D Only at 30 days post-treatment

^E 2 x 4 mL SST gold top tubes. Serum chemistry: Na, K, Cl, CO₂, Ca, fasting glucose, BUN, creatinine, total protein, albumin, total bilirubin, aspartate aminotransferase (AST/SGOT), alanine aminotransferase (ALT/SGPT), alkaline phosphatase, uric acid, Ph, fasting serum lipid profile. Coagulation assessment: 1.8 mL Sodium Citrate light blue top tubes. Coagulation assessment including prothrombin time, partial thromboplastin time, international normalized ratio (PT/PTT/INR).

^F Must be greater than 93% on room air to continue with study procedures

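### The 30-day DLT window has no stated starting dose and outlasts the last required blood count, so a silent grade 3 cytopenia after Visit 6 can be scored as no DLT

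*Combined protocol and SAP*

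**What the plan says.** Section 8.5 defines a DLT as a grade 3 or higher toxicity judged definitely or probably related and "occurring within 30 days of study drug dosing, or as specified per toxicity in the protocol". Sections 8.6 and 8.7 give dose actions by toxicity but no separate DLT window for cytopenias.

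Dosing is described in Section 8.4.1: "All participants receive study drug every 5-9 days for 3 weeks". Appendix 1 makes the CBC unconditional from Visit 2 to Visit 6. Section 10.5 sets the timing of the last of these: "Visit 6: Post-Dosing One-Week Assessment (+/-2 days"). The next visit falls under "Follow-up Visits 7, 8, & 9: 30, 60, and 90 Days Post-Dosing (+/-7 days").

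Three places govern a count at Visit 7:

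- Section 10.6, item 2: "Safety follow-up labs at Visit 7 per PI discretion following Visit 6 labs".
- Appendix 1, footnote B, attached to the Visit 7 CBC: "Only if previous chemistries or coagulation profiles are abnormal or are otherwise clinically indicated".
- Section 9.2.1: "If values are found to be abnormal, a sample will be collected and these parameters re-evaluated at the next study visit".

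DLT and MTD are primary endpoints (Section 5.1), and the 3+3 rule moves to the next dose level when no DLT has been seen (Section 4.1). No section defines a DLT-evaluable participant or the laboratory follow-up needed before someone counts as DLT-free. Dosed participants are not replaced (Section 12.4).

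**The concern.** A 3+3 decision treats an unobserved DLT in the same way as an absent one. A symptom can be reported on any day, but a low platelet or neutrophil count without symptoms is found only if blood is drawn. If required counts stop well before the window closes, a DLT-free result over 30 days is partly an absence of measurement. The error runs in one direction: missed DLTs make escalation more likely and the declared MTD higher, in a trial that enrols children from age 3.

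The protocol itself gives reason to look for laboratory toxicity. Section 1.12 says the main dose-limiting toxicity in its paediatric experience "is grade 3 thrombocytopenia (2 out of 5 participants receiving ABI-009 at 35 mg/m²"). Table 1 predicts rapamycin levels of 7.11 and 14.22 ng/mL at 168 hours after 10 and 20 mg/m², inside the 5-15 ng/mL range that Section 1.13 treats as therapeutic. Drug is thus expected to be present when the last required count is taken. This does not show that counts fall later, but it gives no ground for assuming that they cannot.

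**Working it through.** The plan states no operating characteristics for the escalation rule, so there is no figure to reproduce. The check is a timeline, followed by an illustration.

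**Inputs.** DLT window 30 days (8.5). Three doses, 5-9 days apart, nominally 7 (8.4.1). Visit 6 at 7 ± 2 days after dosing, so Day 5-9 (10.5). Visit 7 at 30 ± 7 days, so Day 23-37 (10.6). I read post-dosing in the visit titles as after the last dose.

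**Window counted from the last dose.** Days without a required count = 30 − Visit 6 day.

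- Nominal: 30 − 7 = 23 days; 23/30 = 77%.
- Range: 30 − 9 = 21 days (70%) to 30 − 5 = 25 days (83%).
- A Visit 7 draw, if taken, can fall from a week before the window closes to a week after.

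**Window counted from the first dose.** Visit 6 day = 2 × dose interval + Visit 6 offset.

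- Nominal: 2 × 7 + 7 = Day 21; 30 − 21 = 9 days.
- Longest gap: 2 × 5 + 5 = Day 15; 30 − 15 = 15 days.
- Shortest gap: 2 × 9 + 9 = Day 27; 30 − 27 = 3 days.
- The earliest Visit 7 is 2 × 5 + 23 = Day 33, so on this reading every on-schedule Visit 7 draw comes after the window has closed.

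**The Visit 7 rules applied to two participants.**

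| CBC at Visit 6 | 9.2.1 | 10.6 item 2 | Footnote B |
|---|---|---|---|
| Abnormal, chemistry and coagulation normal | Repeat required | PI discretion | Only if clinically indicated |
| Normal, no symptoms, chemistry and coagulation normal | Not required | PI discretion | Only if clinically indicated |

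The first row is an inconsistency in wording, but 9.2.1 secures the repeat. The second row is the real gap: no rule requires a count.

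**Chemistry.** Section 10.5 lists Visit 6 chemistry without condition, while Appendix 1 puts footnote B on it. If Appendix 1 governs, required chemistry ends earlier than the required CBC.

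**Illustration of direction only.** Let p be the true DLT rate and s the share of DLTs not measured; both are assumptions. The observed rate is q = p(1 − s). Taking two or more DLTs at a level as stopping escalation, P(escalate) = (1 − q)³ + 3q(1 − q)² × (1 − q)³.

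| p | s = 0 | s = 0.25 | s = 0.50 |
|---|---|---|---|
| 0.25 | 0.60 | 0.74 | 0.86 |
| 0.33 | 0.43 | 0.61 | 0.78 |
| 0.40 | 0.31 | 0.49 | 0.71 |
| 0.50 | 0.17 | 0.35 | 0.60 |

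For example, p = 0.33 and s = 0.25 give q = 0.2475, and 0.426 + 0.420 × 0.426 = 0.605.

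**The case against.** The strongest reply is that monitoring is already reasonable. Counts are roughly weekly through dosing and one week beyond. An abnormal Visit 6 count is repeated under 9.2.1. Clinically indicated tests are always open to the investigator. Families submit a symptom and seizure diary electronically every day (9.1.11, 16.1). AEs are reviewed at Visit 7 (Appendix 1; Section 11.1 asks for this at every visit, though the 10.6 list omits it). Participants discontinued for suspected toxicity are followed at least weekly (11.4), and the DSMB meets before each escalation cohort opens (14).

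Most of this stands, and it narrows the point to new, silent laboratory events after a normal Visit 6 count. It does not remove it. The diary cannot record a platelet count, Section 11.4 does not reach participants who complete all three doses, and the DSMB cannot review a sample that was never drawn.

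A reader might also infer more than the documents support:

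- **That the gap is three weeks as a matter of fact.** This holds only if the window runs from the last dose, which Section 8.5 does not say.
- **That 77% of the window without a count means a similar share of DLTs missed.** The documents give no onset or nadir times, so days without a count do not translate into missed events.
- **That a Day 23 Visit 7 adds a further seven days without contact.** Those days already lie within the 23, and the diary continues through them.
- **That a grade 2 platelet count at Visit 6 would be left unrepeated.** Section 9.2.1 requires the repeat.
- **That the 2 of 5 paediatric rate applies here.** It came at 35 mg/m² in a study combining ABI-009 with temozolomide and irinotecan. The highest level here is 20 mg/m², without those agents.

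**Conclusion.** The point holds in a limited form. The DLT window has no stated starting dose. On either reading it ends after the last required count: by 21-25 days from the last dose, or by about 9 days (3-15) from the first. The three Visit 7 rules do not agree, and none requires a count after a normal Visit 6 result. A silent grade 3 or higher cytopenia in that interval can be scored as no DLT.

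The direction of the effect on escalation and the MTD is upward. Its size is unknown, because it depends on the true DLT rate and on the share of DLTs that are late, silent and unmeasured, and the documents give neither. The escalation probabilities above show sensitivity to assumed values and are not estimates for this trial. The finding does not extend to symptomatic toxicity, and it does not show that cytopenia goes unmonitored during dosing.

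**What to change.** 1. State in Section 8.5 which dose starts the 30-day window.
2. Make the Visit 7 CBC with differential and platelets unconditional. Remove footnote B from that entry in Appendix 1, and align Section 9.2.1 and Section 10.6 item 2 with it.
3. Reconcile Visit 6 chemistry between Section 10.5 and Appendix 1.
4. Align the Visit 7 window with the end of the DLT window, and state how a grade 3 or higher count first found at a Visit 7 draw after Day 30 is scored. This rule is essential if the window runs from the first dose, because an on-schedule Visit 7 then never falls inside it.
5. Count a participant as DLT-free for escalation only once the Visit 7 AE review and CBC are available.

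**Cost.** At most 18 extra samples at an existing visit, 0.5 mL each when drawn alone (Appendix 1, footnote C), some wording changes, and possibly up to a week's delay in a cohort decision.

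**Limit.** A single Visit 7 count is a minimum. It can still miss a fall that recovers between Visits 6 and 7, and the protocol should acknowledge this when it describes a participant as DLT-free.

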8.6 Dose Modification or Discontinuation of Study Drug

For participants who are unable to tolerate the protocol-specified dosing schedule secondary to DLT, dose adjustments are permitted in order to keep the participant on study drug. If administration of ABI-009 must be interrupted due to DLT, drug dosing will be interrupted or modified according to rules described in the table below. Toxicity will be assessed using the NIH/NCI Common Terminology Criteria for Adverse Events, version 5.0. If a participant requires a dose delay of ≥ 3 weeks from the intended day of the next scheduled dose, then the participant must be discontinued from the study or may resume only with the approval of the Principle Investigator.

Table 4: Hematological and non-hematological toxicities and ABI-009 dosing adjustments

TOXICITY	ACTIONS
Non-hematological toxicity	
Grade 2	If the toxicity is tolerable to the participant, maintain the same dose. If

(pneumonitis management detailed separately in 8.7.4)	the toxicity is intolerable to participant, interrupt ABI-009 until recovery to grade 1 or better. Then reintroduce ABI-009 at same dose. If event returns to intolerable grade 2, then interrupt ABI-009 until recovery to grade 1 or better. Then reintroduce ABI-009 at the lower dose level (refer to Table 3). Reintroduction of ABI-009 may occur once.
Grade 3 (except hyperlipidemia*) (pneumonitis management detailed separately in 8.7.4)	Interrupt ABI-009 until recovery to grade 1 or better. Then reintroduce ABI-009 at the lower dose level. For pneumonitis consider the use of a short course of corticosteroids. Reintroduction of ABI-009 may occur once.
Grade 4	Discontinue ABI-009.
Hematological toxicity	
Grade 2 Thrombocytopenia (platelets <75, $\geq 50 \times 10^9/L$)	Interrupt ABI-009 until recovery to grade 1 or better ($>75 \times 10^9/L$). Then reintroduce ABI-009 at initial dose. If thrombocytopenia again returns to grade 2, interrupt ABI-009 until recovery to grade 1 or better. Then reintroduce ABI-009 at the lower dose level (refer to Table 3). Reintroduction of ABI-009 may occur once.
Grade 3 Thrombocytopenia (platelets <50, $\geq 25 \times 10^9/L$)	Interrupt ABI-009 until recovery to grade 1 or better (platelets $\geq 75 \times 10^9/L$). Then resume ABI-009 at one dose level lower. If grade 3 thrombocytopenia recurs, discontinue ABI-009.
Grade 4 Thrombocytopenia (platelets <25 $\times 10^9/L$)	Discontinue ABI-009.
Grade 3 Neutropenia (neutrophils <1, $\geq 0.5 \times 10^9/L$)	Interrupt ABI-009 until recovery to grade 1 or better (neutrophils $\geq 1.5 \times 10^9/L$). Then resume ABI-009 at the initial dose. If ANC again returns to Grade 3, hold ABI-009 until the ANC $\geq 1.5 \times 10^9/L$. Then resume ABI-009 dosing at the lower dose level (refer to Table 3). Discontinue participant from study drug for a third episode of grade 3 neutropenia.
Grade 4 Neutropenia (neutrophils <0.5 $\times 10^9/L$)	Interrupt ABI-009 until recovery to grade 1 or better (neutrophils $\geq 1.5 \times 10^9/L$). Then resume ABI-009 at the lower dose level (refer to Table 3). If grade 3 or grade 4 neutropenia occurs despite this dose reduction, discontinue ABI-009.
Grade 3 febrile neutropenia (not life-threatening)	Interrupt ABI-009 until resolution of fever and neutropenia to grade 1 or better. Hold further ABI-009 until the ANC $\geq 1,500/\text{mm}^3$ and fever has resolved. Then resume ABI-009 at the lower dose level (refer to Table 3). If febrile neutropenia recurs, discontinue ABI-009.
Grade 4 febrile neutropenia (life-threatening)	Discontinue ABI-009.
Any hematological or non-hematological toxicity requiring interruption for ≥ 3 weeks	Discontinue ABI-009.

*Grade 3 hyperlipidemia (hypercholesterolemia and/or hypertriglyceridemia) should be managed using medical therapies.

All interruptions or changes to study drug administration must be recorded.

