6.2 Inclusion Criteria

1. Written informed consent (and assent when applicable) obtained from participant or participant's legal representative
2. Be willing and able to adhere to the study visit schedule and other protocol requirements
3. Male or female ≥ 3 and ≤ 26 years of age at Visit 1
 - b. Because no dosing or adverse event data are currently available on the use of ABI-009 or other mTOR inhibitors in participants <3 years of age, these young children are excluded from this study.
4. Documentation of a diagnosis of medically intractable epilepsy as defined by the failure of at least 2 appropriately dosed and tolerated AEDs to eliminate all clinical seizures over a 6-month period, prior to epilepsy surgery
5. Documentation of resective epilepsy surgery following appropriate pre-surgical evaluation
6. Documentation of continued clinical seizures that persist at least 3 months following resective epilepsy surgery. In order to proceed with enrollment and study drug initiation, participants will have to have had >8 seizures in the last 30 days without 2 consecutive weeks of seizure freedom, as noted by a daily seizure diary.
7. Documentation that the participant is not a candidate for *or* refuses any additional resective epilepsy surgery
8. Participants must have adequate bone marrow function (ANC $\geq 1,000/\text{mm}^3$, platelet count of $\geq 100,000/\text{mm}^3$, and hemoglobin $\geq 9 \text{ gm/dL}$) before study drug dosing.
9. Participants must have adequate liver function (SGPT/ALT ≤ 5 times ULN and bilirubin ≤ 5 times ULN) before study drug dosing.
10. Participants must have adequate renal function, defined as: Creatinine clearance or radioisotope GFR $\geq 70\text{mL/min}/1.73 \text{ m}^2$ **or** a serum creatinine before study drug dosing based on age/gender as follows:

Age	Maximum Serum Creatinine (mg/dL)	
	Male	Female
3 to < 6 years	0.8	0.8
6 to < 10 years	1	1
10 to < 13 years	1.2	1.2
13 to < 16 years	1.5	1.4
≥ 16 years	1.7	1.4

The threshold creatinine values in this table were derived from the Schwartz formula for estimating GFR utilizing child length and stature data published by the CDC.

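### Table 4's two grade 2 rows each describe two reintroductions of ABI-009 but close with a limit of one, so it is unclear whether the second is allowed.

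*Combined protocol and SAP*

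**What the plan says.** Table 4 in section 8.6 gives one row per toxicity type and grade.

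- **Grade 2 non-hematological, if not tolerable.** After the first interruption and recovery, the row reads: "Then reintroduce ABI-009 at same dose. If event returns to intolerable grade 2, then interrupt ABI-009 until recovery to grade 1 or better". It then continues: "Then reintroduce ABI-009 at the lower dose level (refer to Table 3). Reintroduction of ABI-009 may occur once".
- **Grade 2 thrombocytopenia.** The first restart is at the starting dose: "Then reintroduce ABI-009 at initial dose. If thrombocytopenia again returns to grade 2, interrupt ABI-009 until recovery to grade 1 or better". The row then closes with the same two sentences, a lower-level restart and the limit of one.
- **Grade 3 non-hematological.** One restart is described, at the lower level, and the row ends: "For pneumonitis consider the use of a short course of corticosteroids. Reintroduction of ABI-009 may occur once". Description and limit agree.
- **Grade 3 neutropenia.** Two restarts are described (initial dose, then lower level). The stopping point is explicit: "Discontinue participant from study drug for a third episode of grade 3 neutropenia".

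Other provisions that bear on the point:

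- Section 4.1 plans three weekly infusions.
- Section 15.1.1 limits the per-protocol set to participants who completed more than 80% of doses without a major violation.
- Section 15.4 tabulates permanent discontinuation of study drug as a primary tolerability analysis.
- Section 8.5 restricts DLTs to toxicity of grade 3 or higher.
- For a delay of three weeks or more, the section 8.6 text provides for discontinuation but leaves room to resume if the principal investigator approves. The last row of Table 4 and section 11.4 give discontinuation with no such exception.

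**The concern.** A site following either grade 2 row reaches an instruction to restart at the lower level and then, in the next sentence, a limit that the first restart may already have used up. Two participants with the same sequence of counts or symptoms could be handled differently, and both decisions could be defended from the same row.

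At stake are whether the third infusion is given, whether the participant is tabulated as having permanently discontinued, and whether the participant enters the per-protocol set. The first is a dosing decision. The second feeds a primary tolerability result, in cohorts of three to six where one participant is a large fraction.

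The three-week provisions add a second uncertainty of the same kind. A participant who recovers slowly must stop under Table 4 and section 11.4, but may resume with approval under the section 8.6 text.

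**Working it through.** There is no stated figure to reproduce. The check is a count of restarts per row against that row's own limit, followed by the effect on doses received.

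**1. Restarts described against the stated limit (Table 4)**

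| Row | Restarts described | Stated limit | Agree? |
|---|---|---|---|
| Grade 2 non-hematological | 2 (same dose, then lower) | one | unclear |
| Grade 2 thrombocytopenia | 2 (initial dose, then lower) | one | unclear |
| Grade 3 non-hematological | 1 (lower) | one | yes |
| Grade 3 thrombocytopenia | 1 (lower) | stop on recurrence | yes |
| Grade 3 neutropenia | 2 (initial, then lower) | stop at third episode | yes |
| Grade 4 neutropenia | 1 (lower) | stop on recurrence | yes |
| Grade 3 febrile neutropenia | 1 (lower) | stop on recurrence | yes |

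The problem is confined to two rows.

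**2. Can the second restart occur?** Three infusions leave 3 − 1 = 2 gaps, so at most two restarts can be followed by a dose. The path is: Dose 1, toxicity, restart at the unchanged dose (Dose 2), recurrence, restart at the lower level (Dose 3). It fits the course exactly.

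**3. What each reading does to the row**

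- Limit covers all restarts: Dose 2 uses it, and the lower-level instruction just before the limit can never be carried out.
- Limit covers only the lower-level restart: the first such restart is Dose 3. A second would need a fourth infusion, so the limit never binds in a three-infusion course.

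Neither reading gives both sentences something to do.

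**4. Doses received when toxicity recurs after Dose 2**

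- Limit on all restarts: 2/3 = 66.7%, below the cut of more than 80%. With three doses only 3/3 passes.
- Limit on the lower-level restart only: 3/3 = 100%.

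Cumulative dose under the two readings, using the levels in Table 3 (mg/m²):

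| Level | Two infusions | Three infusions, last one level lower |
|---|---|---|
| 1 | 5 + 5 = 10 | 10 + 2.5 = 12.5 |
| 2 | 10 + 10 = 20 | 20 + 5 = 25 |
| 3 | 20 + 20 = 40 | 40 + 10 = 50 |

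The 3/3 figure assumes that a held infusion is postponed, as the dose-delay wording in section 8.6 suggests. If a held infusion were forfeited instead, with Dose 2's slot lost and the restart in the third slot, both readings would give 2/3 and the limit would not matter.

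**5. Effect on the tolerability tabulation.** One such participant changes the discontinuation proportion from 0/3 to 1/3 = 33% in a cohort of three, or from 0/6 to 1/6 = 17% in a cohort of six.

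**The case against.** The best defense is that the limit follows directly on the lower-level restart and can be read as applying to that step alone. On that reading the row is a workable sequence: same dose, then lower dose once, then stop. It also avoids making a sentence cancel the instruction before it. This is a possible reading, but the table does not state it. The grade 3 non-hematological row uses the same sentence where one restart is the total. Where two restarts are clearly meant, in the grade 3 neutropenia row, the table gives a stopping point that fits two. The grade 3 comparison does not settle the matter, since its only restart is also at the lower level. So the ambiguity stands, and this review does not resolve it.

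Two further objections limit the size of the point, and both stand. First, the path needs two grade 2 episodes with recovery inside a three-infusion course, and the documents give no frequency for that. The shift from 0% to 33% is simply what any single event does in a cohort of three. Second, the study has one site, which reduces the scope for inconsistent handling.

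A reader might cite section 1.12, which names thrombocytopenia as the main dose-limiting toxicity in children. That passage concerns grade 3 events, in 2 of 5 participants at 35 mg/m² in a trial that also gives temozolomide and irinotecan. The highest level here is 20 mg/m², and the grade 3 thrombocytopenia row is clear. It does not show how often the grade 2 row will be used.

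**Conclusion.** The concern holds for the two grade 2 rows. Each describes two restarts and permits one. For a participant whose toxicity recurs after Dose 2, the reading decides between 3/3 and 2/3 (67%) of infusions, and with that per-protocol eligibility and classification as a permanent discontinuation. This rests on held infusions being postponed. How many participants would be affected cannot be estimated from the documents.

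The conflict over delays of three weeks or more, between the section 8.6 text on one side and Table 4 and section 11.4 on the other, also holds.

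Four stronger inferences are not supported:

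- **Table 4 as a whole is unusable.** The other rows listed above have limits that fit the steps they describe.
- **DLT counts or the MTD are distorted.** A DLT must be grade 3 or higher, so a grade 2 event is not counted. The only link is indirect: a third infusion is additional exposure.
- **The neutrophil figures contradict each other.** Criterion 8 in section 6.2 ("Participants must have adequate bone marrow function") admits an ANC of 1,000/mm³ = 1.0 × 10⁹/L, while resumption after grade 3 neutropenia needs 1.5 × 10⁹/L, which is 0.5 × 10⁹/L or 50% higher. A participant who enters at 1.0 to below 1.5 and falls below 1.0 must exceed the minimum for entry, and possibly their own entry value, to resume. But the two figures govern different decisions, first dosing and resumption after toxicity, and both can be followed. At most the sponsor could confirm that the difference is intended.
- **The third-episode clause for neutropenia is a dosing problem.** Recovery and re-dosing come between episodes, so a third can follow only the third infusion, when no dosing is left to stop. The clause changes nothing.

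**What to change.** 1. In each of the two grade 2 rows of Table 4, the sponsor and investigator should reconcile the described sequence with the closing limit, so that the row says plainly how many restarts are allowed and which steps the limit counts. Which rule should govern is for them to decide.
2. Reconcile the section 8.6 text, the last row of Table 4 and section 11.4 on delays of three weeks or more.
3. Optionally, confirm that the difference between the entry and resumption neutrophil figures is intended.
4. If any participant has already been managed under a grade 2 row, record which reading was applied, so that the section 15.4 tabulation and the per-protocol set can be interpreted.

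Items 1 and 2 cost amendment wording in Table 4, section 8.6 and section 11.4. They need no new visits, data or participants. Item 3 needs only a statement; if a figure were changed, criterion 8 appears in both the synopsis and section 6.2.
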